4.2 Screening and Enrollment

Subjects enrolled in this study will be males and females, ≥ 9 to ≤ 17 years of age, with axillary hyperhidrosis who participated and completed treatment in Study BBI-4000-CL-105. Up to 24 subjects may participate in this study.

4.3 Screen Failure

A subject who has been screened but subsequently fails to meet the inclusion/exclusion criteria prior to receipt of study drug in this study will be deemed a screen failure.

4.4 Completion

Each subject will participate in the study for up to approximately 26 weeks, from the time the informed consent form (ICF) is signed/assent provided (Visit 1) through the final visit (Week 26 [Day 182 (± 5 days)]).

4.5 Early Termination (ET)

A subject or the subject's parent/guardian may withdraw the subject from treatment or from the study at any time upon request or the subject may be withdrawn at any time at the discretion of the Investigator or Sponsor for safety, behavioral, or administrative reasons.

4.5.1 Criteria for Premature Discontinuation

4.5.1.1 Discontinuation from Treatment

A subject must be permanently discontinued from the study drug for any of the following reasons:

- The subject becomes pregnant.
- Allergic or adverse reaction to the study drug.
- Clinically significant AE, which in the opinion of the Investigator, or SRC, would put the subject at unnecessary risk if dosing was continued.
- The subject's axillary hyperhidrosis worsens and requires alternative or supplemental medication during the study.

If a subject is discontinued from treatment, he or she should continue to be followed in the study per the [SCHEDULE OF ACTIVITIES](#). If subject refuses to stay in the study, then he or she will be encouraged to complete the Early Termination Visit 7 study procedures.

4.5.1.2 Discontinuation from Study

A subject must be discontinued from study drug and from the study for the following reason:

- The subject withdraws consent. From the time consent is withdrawn, no additional data should be collected. However, the Sponsor may retain and continue to use data collected before such withdrawal of consent.

A subject may be discontinued from the study drug or from the study for the following reason:

- The subject requests withdrawal from the study. For the safety of the subject, if withdrawal is requested, the subject should be encouraged to complete the Early Termination Visit 7 study procedures.

4.5.1.3 Lost to Follow-up

A subject is considered to have been lost to follow-up if he/she [subject or parent/legal guardian] cannot be contacted by the Investigator (or designee) after 3 documented attempts. The Investigator (or designee) will document efforts to attempt to reach the subject/parent/guardian. The end of participation for a subject lost to follow-up is documented as the date of the last visit.

4.5.1.4 Subject Replacement

Subjects who prematurely discontinue will not be replaced.

4.6 Safety Oversight

4.6.1 Study Review Committee (SRC)

An internal SRC, comprising the Sponsor Medical Monitor, Lead Investigator and CRO Medical Monitor, will facilitate the management and identification of potential safety concerns and will assess whether revisions to the study protocol and/or consent are required and will evaluate the overall progress of the study.

4.6.2 Investigator

The Investigator must have access and be available to promptly review the results of all safety assessments (i.e., clinical laboratory testing), ECG results, vital signs and AEs including application site assessment information throughout the study. Safety assessments must be promptly entered into the Electronic Data Capture (EDC) system (if possible, within 48 hours of notification of event). Clinical laboratory data will be evaluated by the Investigator and clinical relevance will be assessed for abnormal values and the assessment will be documented on the laboratory report. A copy of the reports will be maintained as part of the source documentation.

5 STUDY SUBJECT SELECTION

5.1 Inclusion Criteria

For a study subject to be evaluated for study participation:

1. Written Informed Consent (including HIPAA) will be obtained from the Parent(s)/Legal Guardian(s) prior to the conduct of any study related procedures to permit participation of a minor in a clinical research study in accordance with federal and local laws. Additionally, assent from a minor child will be obtained in accordance with federal and local laws as well as in compliance with the recommendations of the approving Institutional Review Board (IRB)/Institutional Ethics Committee (EC).

Study subjects will be eligible for inclusion in the study if they meet all the following criteria at Screening/Enrollment (Week 0 [Day 1]) as applicable:

2. Are male or female ≥ 9 to ≤ 17 years of age at the time of consent.
3. Have enrolled and completed treatment in Study BBI-4000-CL-105 and met all inclusion/exclusion criteria, were compliant with study procedures (e.g., visits and PK sample collection) and did not experience any clinically significant AEs that would preclude safe continuation of study drug for up to an additional 24 weeks.
4. Continue to be in generally good health based on Investigator's assessment (other than axillary hyperhidrosis), with no clinically significant laboratory abnormalities, co-morbidities or psychiatric conditions which, in the opinion of the Investigator, would place the subject at increased risk or would confound the objectives of the study.
5. The Parent(s)/Legal guardian(s) and study subject are willing and able to follow all study-related procedures, including but not limited to application of study drug and venipuncture and are willing and able to return to the study clinic for required study visits.
6. If female, must be willing to take monthly pregnancy tests during the study.
7. Sexually active females must agree to use a medically acceptable method of contraception while receiving study drug. For purposes of this study, all female subjects are considered of childbearing potential as axillary hyperhidrosis generally occurs in post-pubescent individuals. Acceptable contraceptive methods include the following:
 - a. Abstinence for the duration of the study or where partner is sterile (e.g., vasectomy) is an acceptable form of contraception.
 - b. Hormonal contraception, including oral, injectable, or implantable methods started at least 2 months prior to screening, or
 - c. Two forms of non-hormonal contraception, including intrauterine devices (IUD) (at least 1-week status post placement) and properly used barrier methods (e.g., male or female condoms, cervical cap/diaphragm, spermicidal agents, etc.).

The Investigator will educate the subject regarding abstinence or contraception options and the correct and consistent use of effective contraceptive methods in order to successfully prevent pregnancy.

5.2 Exclusion Criteria

A study subject will be excluded from the study if they meet any of the following criteria at Screening/Enrollment (Week 0 [Day 1]).

1. In the Investigator's opinion, any clinically significant systemic or local skin reaction related to use of the study drug.
2. Subcutaneous tissue conditions of the axilla(e), (i.e., the axillary area should be deemed otherwise "normal", besides the hyperhidrosis diagnosis, and free of blisters, large boils or sinus tracts, significant scarring or open wounds).
3. Has received any prohibited medication(s) or procedure(s) under Study BBI-4000-CL-105 prior to Screening/Enrollment.
4. Subject is pregnant, lactating or is planning to become pregnant during the study.
5. Positive drug or alcohol screen while enrolled in Study BBI-4000-CL-105.

6 DESCRIPTION OF STUDY PROCEDURES

A description of study procedures and frequency are listed in the [SCHEDULE OF ACTIVITIES](#) and is provided within the content of this protocol.

6.1 Obtaining Informed Consent

6.1.1 Written Parental/Legal Guardian Consent

Adequate provisions must be made for soliciting the permission of the subject's parent(s) or legally authorized representative/guardian. If a subject turns 18 years of age during the course of the study, written informed consent will be obtained from the subject at the next visit.

The process for obtaining oral and/or written assent for children and adolescents is similar to that of obtaining consent for adults. An effective informed consent process involves at minimum these elements:

- Conducting the process in a manner and location that ensures privacy;
- Giving adequate information about the study in a language understandable to the parent/legal guardian and child/adolescent;
- Providing adequate opportunity for the parent/legal guardian and child/adolescent to consider all options;
- Responding to the parent(s)/legal guardian(s) and child's/adolescent's questions;
- Ensuring the parent/legal guardian and child/adolescent has understood the information provided;
- Obtaining the parent/legal guardian and child/adolescent voluntary agreement to participate, and
- Continuing to provide information to parent(s)/legal guardian(s), child/adolescent as new information regarding this research program becomes available that may affect their willingness to continue in this study.

6.1.2 Minimum Federal Requirements for Consent

The Institutional Review Board (IRB)/Independent Ethics Committee (IEC) will determine the permissions (one or both parents/legal guardian(s)) required for participation of a minor in this study based on level of risk (e.g., minimal or greater than minimal).

6.1.3 When Parents/Legal Guardians Disagree

If there are two parents/legal guardians available to give permission but they disagree about allowing their child to participate in the study, the child may not be enrolled unless that disagreement can be resolved. This applies even if only one parent's (guardian's) signature is required. When both parents (guardians) are involved in the decision, they must agree for the child to be enrolled. If a parent who was not involved or available for the original consent later becomes involved or available, the two parents (guardians) must then agree.

6.1.4 Assent

The Investigator should carefully consider and propose adequate provisions for obtaining assent of children and adolescents prior to their participating in research. In general, assent is usually obtained from a child ≥ 7 years of age, however the approving IRB/IEC will determine whether or how assent will be obtained. The child should be provided with essential information and asked if they wish to participate in the research study.

6.1.5 Documenting the Consent/Assent Process

Consent/Assent MUST be obtained and documented PRIOR to initiation of any study procedures. The Principal Investigator or his/her approved designee must explain the nature of the study and associated risks to the parent(s)/legal guardian and study subject. The date/time that the informed consent is signed, a brief description of the consent/assent process (e.g., questions asked by the subject), and the name of the individual who obtained consent will be recorded in the source record. A copy of the signed informed consent should be provided to the parent(s)/legal guardian. Depending on the approving IRB and local requirements, an assent form may be included as part of the consent and may or may not be required to be signed by the child. Investigators must adhere to their local requirements for proper documentation of consent/assent. A summary of assent procedures for execution of this study must be maintained in the Investigator Essential Regulatory File. It is the responsibility of the Principal Investigator to ensure that any individual delegated the responsibility for obtaining consent/assent are familiar and adhere to the applicable consent/assent requirements.

6.2 Demographics

Subject demographic information will be recorded at Screening/Enrollment (Week 0 [Day 1]). Demographic information will include date of birth, gender (at the time of birth), race, and ethnicity. Findings will be documented in the source documentation and the eCRF.

6.3 Histories

6.3.1 General Medical/Surgical and Social History

Relevant medical and surgical history will be recorded at Screening/Enrollment (Week 0 [Day 1]) and will include medical diagnoses, major surgical procedures within the last 3

years. Social history (i.e., tobacco, drug, and alcohol use) and allergies (i.e., food, medications and environmental) will also be recorded at screening. Findings will be documented in the source documentation and the eCRF.

6.3.2 History – Hyperhidrosis

The parent/guardian and subject will provide historical information pertaining to the diagnosis of axillary hyperhidrosis, including date of diagnosis.

6.3.3 Medication History

Medications taken within the last month (30 days) prior to first dose of sofrironium bromide gel, 15% under Study BBI-4000-CL-105 and within 1 week prior to Screening/Enrollment (Week 0 [Day 1]) will be recorded in the source document and on the eCRF. Also refer to [Section 6.13](#) concomitant medications and restrictions for additional information.

6.4 Abbreviated Physical Examination

The abbreviated physical examination will include an examination of general appearance, skin (including specific evaluation of axillary vaults), lungs, and heart. Additional systems will be evaluated as needed. Physical exam findings must be recorded in the source documentation and include the date and name of the individual conducting the examination. Physical examinations must be performed by an individual licensed to conduct standard physical examinations. An examination will be done at every visit.

6.5 Height and Weight

Height and weight will be collected at Baseline, prior to first dose, collected under BBI-4000-CL-105, and will be carried over to the current study.

6.6 Application Site Tolerability Assessment

Application site tolerability assessments will be evaluated through assessment of symptoms at the drug-application site. These assessments are to be performed for each axilla individually. Subject assessments will be made prior to the Investigator assessments ([Appendix F](#)).

Subject Local Tolerability Assessments: Subjects will be queried about whether any symptoms of burning, stinging, or itching occurred at the drug-application site within the previous 24 hours and further whether any such symptoms persisted longer than 1 hour following study drug application. Standardized scales will be used to describe specifically the severity of any burning, stinging or itching ([Appendix F](#)).

Investigator Local Tolerability Assessments: Investigators will observe for the existence of any significant local symptoms of scaling or erythema at the drug-application site. Significant local symptoms are defined as those not ordinarily observed following application of a topical product. Standardized scales will be used to describe specifically the severity of any erythema or scaling ([Appendix F](#)).

Local tolerability signs and symptoms that result in the subject's requiring a concomitant therapy, interruption of treatment, or discontinuation from the study, will also be reported as an AE.

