3.2 Criteria for Evaluation

3.2.1 Primary Endpoints

3.2.1.1 Safety

- Incidence and severity of application site burning, itching, stinging, scaling and erythema
- Incidence and severity of all AEs and their relationship to study drug
- Incidence of clinically meaningful change from baseline in safety laboratory parameters, 12-lead electrocardiograms (ECGs) and vital signs
- Proportion of subjects who discontinue treatment due to an AE

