APPENDIX F APPLICATION SITE TOLERABILITY ASSESSMENTS

These assessments are to be performed for each axilla individually. The designation of “Right Axilla” or “Left Axilla” in the source documents and eCRFs refers to the subject’s right and left axilla respectively in all cases. Subject assessments are to be performed prior to Investigator assessments.

Local Tolerability (Subject): As reported by the Subject to the Investigator, the severity of any symptoms of burning, stinging or itching at the application-site within the previous 24 hours and further any such symptoms persisting longer than 1 hour following study drug application will be described specifically by severity using the following standardized scales:

Score	Burning	Stinging	Itching
0 = Absent	Normal, no discomfort	Normal, no discomfort	Normal, no discomfort
1 = Minimal	An awareness, but no discomfort	An awareness, but no discomfort	An awareness, but no discomfort
2 = Mild	Noticeable discomfort causing intermittent awareness	Noticeable discomfort causing intermittent awareness	Noticeable discomfort causing intermittent awareness
3 = Moderate	Noticeable discomfort causing continuous awareness	Noticeable discomfort causing continuous awareness	Noticeable discomfort causing continuous awareness
4 = Severe	Definite discomfort causing continuous awareness, interfering occasionally with normal daily activities	Definite discomfort causing continuous awareness, interfering occasionally with normal daily activities	Definite discomfort causing continuous awareness, interfering occasionally with normal daily activities

Local tolerability (Investigator): The Investigator will assess the drug-application site for the existence of significant local symptoms. Significant local symptoms are defined as those not ordinarily observed following application of a topical product. The following standardized scales will be used to describe specifically the severity of any erythema or scaling:

Score	Scaling	Erythema
0 = Absent	No scaling	No redness
1 = Minimal	Fine scaling, barely perceptible	Faint red or pink coloration, barely perceptible
2 = Mild	Slight scaling, noticeable only with light scratching	Light red or pink coloration
3 = Moderate	Definitely noticeable scaling	Medium red coloration
4 = Severe	Extensive scaling	Beet red coloration

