### 13.3 Primary Analyses

#### 13.3.1 Safety

Safety evaluations will consist of AEs, application site local tolerability, physical examinations, vital signs, ECGs, and laboratory measurements (hematology, chemistry, and urinalysis).

- Adverse events:
  - Adverse events will be mapped to standard terms, i.e., MedDRA System Organ Class and Preferred Term.
  - Adverse events that occurred during the screening period will be listed separately and will not be included in the AE tabulations.
  - Adverse events that start on or after first dose will be considered a TEAE. At each post-baseline visit, the number and proportion of subjects reporting any given TEAE will be tabulated by severity; each subject will be counted only once according to the worst severity reported up to the current visit. Separate tables will be constructed for (a) all reported TEAEs, (b) protocol treatment related TEAEs, (c) serious TEAEs, and (d) TEAEs leading to protocol treatment discontinuation.
- At each applicable visit, local tolerability (burning, itching, stinging, scaling, and erythema at either axilla) will be described by severity as defined in Appendix E. Subject and Investigator assessments will be included in separate tables and listings, with the count and percentage of subjects within each severity (maximum severity assessed at either axilla) presented by parameter and visit.
- Vital signs will be summarized similarly as for laboratory parameters but without shift tables.
- Laboratory parameters will be descriptively summarized (mean, SD, median, minimum, maximum) for values at each visit and for changes from baseline at each subsequent visit. In addition, at each post baseline visit, parameter status (low, normal, high) will also be summarized as shift tables vs. baseline status.
- Descriptive statistics and/or frequency tables will be prepared as appropriate for physical examinations, and ECG (HR, QTcF, PR, and QRS) parameters, and abnormalities (e.g., normal; abnormal, not clinically significant; abnormal, clinically significant).
- Concomitant medications will be mapped according to the World Health Organization Drug Dictionary (WHODD) and will be presented in data listings.

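### Conflicting instructions on erythema and scaling let sites leave out mild signs they judge ordinary, although the primary endpoint has no such threshold

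*Protocol*

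**What the plan says.** The first primary safety endpoint (Protocol 3.2.1.1, repeated in SAP 7.2.1.1) is "Incidence and severity of application site burning, itching, stinging, scaling and erythema". It sets no minimum severity and no test of expectedness.

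Protocol 6.6 splits the assessment in two. For the subject's part, "Subjects will be queried about whether any symptoms of burning, stinging, or itching occurred at the drug-application site within the previous 24 hours". For the investigator's part, "Investigators will observe for the existence of any significant local symptoms of scaling or erythema at the drug-application site", and the next sentence defines the qualifier: "Significant local symptoms are defined as those not ordinarily observed following application of a topical product". The sentence after that says "Standardized scales will be used to describe specifically the severity of any erythema or scaling".

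Protocol Appendix F repeats the restriction directly above the grading table: "The Investigator will assess the drug-application site for the existence of significant local symptoms". SAP Appendix E carries the same text. The table runs from 0 (absent) to 4 (severe), and grade 1 for scaling reads "Fine scaling, barely perceptible". SAP 13.3.1 reports the scores "with the count and percentage of subjects within each severity (maximum severity assessed at either axilla) presented by parameter and visit".

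**The concern.** The qualifier turns on whether a sign is expected with a topical product, not on how severe it is. Faint redness or fine scaling is the kind of finding an investigator could call ordinary for a topical product, yet the scale has a grade for it and the SAP plans to count that grade. An investigator who takes the definition at face value could pass over such a sign. One who takes the following sentence at face value would grade it.

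Neither document defines what is ordinary after a topical product. All subjects receive active drug, so no vehicle arm can show it. The judgement falls to each investigator, at up to 10 sites (Protocol synopsis). At stake are two of the five components of a primary safety endpoint, in a study of at most 24 children and adolescents where a few cases shift the reported percentage noticeably.

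**Working it through.** The plan has no figure to reproduce. Neither document gives an expected incidence of erythema or scaling, and 24 is the enrollment ceiling of the parent study (Protocol 11.1), with no power calculation behind it. The check is therefore of the text, followed by an illustration.

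**The statements side by side**

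| Place | What it covers | Threshold |
|---|---|---|
| Protocol 3.2.1.1; SAP 7.2.1.1 | Endpoint: incidence and severity of all five components | None |
| Protocol 6.6, subject part | Burning, stinging, itching: any symptom | None |
| Protocol 6.6; Protocol Appendix F; SAP Appendix E: what to look for | Scaling, erythema | Beyond what is ordinary for a topical product |
| Same three places: what the scale describes | Any erythema or scaling | None |
| Grading table (both appendices) | 0 = none; 1 = barely perceptible | None |
| SAP 13.3.1 | Count and percentage in each grade, by visit | None |

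1. Only one row has a threshold, but it is the row that tells the assessor what to look for, and it appears three times.
2. Take a subject with faint pink coloration that the investigator regards as usual after a gel. Under the look-for sentence, this is not a finding the investigator was asked to identify. Under the grading sentence, it is grade 1. No other text resolves the conflict.
3. If the sign is passed over, it reaches the SAP 13.3.1 table as grade 0 or as missing. Either way it is lost from the count of affected subjects.
4. The other safety routes do not reliably recover it. Protocol 6.6 requires a tolerability sign to be reported as an adverse event when it leads to concomitant therapy, treatment interruption or discontinuation. The abbreviated physical examination covers the axillary vaults (Protocol 6.4) but does not use the 0–4 scale. Protocol 6.4 places that examination at every visit, whereas the Schedule of Activities shows it only at Weeks 0, 4, 24 and 26.

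**Illustration (both inputs are assumptions)**

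Let p be the true proportion of subjects with any erythema or scaling, and f the share of those subjects whose signs go unrecorded because they are judged ordinary. With N = 24 and subjects treated as independent:

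- recorded proportion q = p × (1 − f)
- expected recorded cases = 24 × q
- chance that no case is recorded = (1 − q)^24

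For p = 20% and f = 50%: q = 0.20 × 0.50 = 0.10; expected cases = 24 × 0.10 = 2.4; chance of none = 0.90^24 = 8.0%.

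Each cell gives expected recorded cases, then the chance of recording none:

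| p | f = 0 | f = 25% | f = 50% | f = 75% |
|---|---|---|---|---|
| 10% | 2.4; 8.0% | 1.8; 15.4% | 1.2; 29.2% | 0.6; 54.5% |
| 20% | 4.8; 0.5% | 3.6; 2.0% | 2.4; 8.0% | 1.2; 29.2% |
| 30% | 7.2; about 0% | 5.4; 0.2% | 3.6; 2.0% | 1.8; 15.4% |

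If only grades 1–2 are at risk, f is the share of affected subjects whose worst grade is 1–2, multiplied by the fraction of those passed over. So f = 75% needs at least three quarters of affected subjects to have nothing worse than grade 2. The documents give neither factor.

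**The case against.** The strongest reply is that the instrument, read as a whole, already asks for everything to be graded. The sentence after the definition refers to any erythema or scaling. Grade 0 is anchored as no scaling and no redness, so scoring a visibly pink axilla as 0 would contradict the scale. Grade 1 would have little use if only unusual findings were scored, and the SAP tabulates every grade. Nowhere is an investigator told to omit an ordinary sign or to score it 0. On this view the fault is a loose introductory sentence. Three of the five components are unaffected, and the analysis is descriptive.

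Most of this stands. It rules out a stronger reading that a reader might infer: that investigators are told to record significant signs only, so that the primary endpoint will be under-recorded. The documents do not support that reading, because the grading sentence and the grade 0 anchor point the other way. Nor do they support a claim that mild grades are the commonest on this scale. Protocol 1.3 describes most adverse events in earlier studies as mild, which is not a statement about tolerability grades.

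The reply does not remove the conflict. A defined restriction placed directly above the scale is still an instruction, and a careful investigator could follow either sentence and claim compliance.

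**Conclusion.** The three places contradict themselves on which erythema and scaling are ascertained, and the restricting sentence does not match the endpoint, the low end of the scale or the planned tables. The consequence is a risk of under-recording mild signs and of sites applying different rules, limited to scaling and erythema. It is not a demonstrated loss of data.

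The size is unknown. The illustration shows only that, with 24 subjects, leaving out a few mild cases could change the tolerability picture. At an assumed 20% incidence, losing half the affected subjects takes 4.8 expected cases to 2.4. This rests on assumed p and f, full enrollment and independence between subjects. If every investigator grades every visible sign, f is zero and nothing is lost.

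The correction is worth making because the wording bears on a primary endpoint and can be repaired by deletion.

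**What to change.** In Protocol 6.6, Protocol Appendix F and SAP Appendix E, delete the word significant and its definition. Replace them with a statement that all erythema and scaling are graded 0–4 for each axilla at every scheduled tolerability assessment, whether or not the sign is expected with a topical product. If a judgement of significance is wanted, collect it in a separate field so that it does not decide whether a grade is entered.

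The text should say every scheduled tolerability assessment, not every visit. The Schedule of Activities has no tolerability assessment at Visit 8, while the synopsis and SAP 7.3.1 list Week 26 only if applicable.

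Changing the SAP alone would not help, because the problem lies in what is recorded at the visit. The protocol text has to change as well, through the amendment process in Protocol 13.1.

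The change adds no visit or procedure. Recorded incidence may rise slightly. Week 0 tolerability scores are carried over from Study BBI-4000-CL-105, whose wording is not in these documents and may differ. That should be noted wherever shifts from Week 0 are read, including the scaling and erythema shift tables listed in SAP Appendix A.
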